Appendix 10 Management of Cobimetinib plus Atezolizumab-Associated Adverse Events (Arm A) (cont.)

Table 2 Guidelines for Managing Atezolizumab and Cobimetinib–Associated Hepatotoxicity (cont.)

Event	Action to Be Taken
AST/ALT > 3 × ULN with bilirubin > 2 × ULN	
 • Withhold atezolizumab and cobimetinib. • Consult hepatologist and consider liver biopsy. • Consider administering 1–2 mg/kg/day oral prednisone or equivalent followed by ≥ 1 month taper (for possible autoimmune hepatitis). • If LFTs do not decrease within 48 hours after initiation of systemic steroids, consider adding an immunosuppressive agent (e.g., mycophenolate mofetil or TNF-α antagonist). • Monitor LFTs every 48–72 hours until decreasing and then follow weekly. • Restart atezolizumab at fixed dose and cobimetinib at 1 dose reduction after discussion with medical monitor if AST/ALT < 3 × ULN with bilirubin < 2 × ULN and steroid dose < 10 mg oral prednisone equivalent per day.^{a, b, c} • Permanently discontinue atezolizumab and cobimetinib for life-threatening hepatic events, and contact the Medical Monitor.
AST/ALT > 10 × ULN	
 • Permanently discontinue atezolizumab and cobimetinib.^c • Consult hepatologist and consider liver biopsy. • Consider administering 1–2 mg/kg/day oral prednisone or equivalent (for possible autoimmune hepatitis). If event resolves to Grade 1 or better, taper corticosteroids over ≥ 1 month. • If LFTs do not decrease within 48 hr after initiation of systemic steroids, addition of an alternative immunosuppressive agent (e.g., mycophenolate mofetil or TNF-α antagonist) or dose escalation of corticosteroids may be considered. • Monitor LFTs every 48–72 hours until decreasing and then follow weekly.

LFT = liver function test; Q4W = every 4 weeks; ULN = upper limit of normal.

^a If corticosteroids have been initiated, they must be tapered over ≥ 1 month to ≤ 10 mg/day oral prednisone or equivalent before atezolizumab can be resumed.

^b Atezolizumab may be withheld for a period of time beyond 105 days to allow for corticosteroids to be reduced to ≤ 10 mg/day oral prednisone or equivalent. The acceptable length of the extended period of time must be agreed upon by the investigator and the Medical Monitor.

^c Resumption of atezolizumab may be considered in patients who are deriving benefit and have fully recovered from the immune-mediated event. Patients can be rechallenged with atezolizumab only after approval has been documented by both the investigator (or an appropriate delegate) and the Medical Monitor.

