4.6.2 Study Treatment Discontinuation

Patients must permanently discontinue study treatment if they experience any of the following:

- Confirmed disease progression or loss of clinical benefit (see Section 3.1.2 for dosing beyond progression)
- Symptomatic deterioration attributed to disease progression, as determined by the investigator, after integrated assessment of radiographic data, biopsy results, and clinical status
- Intolerable toxicity related to any study drug
- Any medical condition that the investigator or Sponsor determines may jeopardize the patient's safety if he or she continues to receive study treatment
- Use of another non-protocol-specified anti-cancer therapy (see Section 4.4.2)
- Pregnancy
- Withdrawal of consent
- Investigator or Sponsor determines it is in the best interest of the patient (e.g., unwillingness to comply with study assessments that compromise their safety)
- Any adverse event that requires study treatment discontinuation per the guidelines in Section 5.1, Appendix 10, and Appendix 11.

- In cases where discontinuation of one study drug is required for toxicity, patients may continue on the remaining drug (Arm A only) per the guidelines in Section 5.1 and Appendix 10.

The primary reason for study drug discontinuation should be documented on the appropriate eCRF. Patients who discontinue study treatment will not be replaced.

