Appendix 10 Management of Cobimetinib plus Atezolizumab-Associated Adverse Events (Arm A)

Note: For information regarding management of atezolizumab-associated adverse events, please refer to [Appendix 11](#).

Guidelines for Management of Cobimetinib plus Atezolizumab Adverse Events

Event	Action to Be Taken
General guidance for dose modifications and treatment delays and discontinuation	
 • There will be no dose modifications for atezolizumab. • If atezolizumab is withheld and corticosteroids are initiated for an atezolizumab-related toxicity, corticosteroids must be tapered over ≥ 1 month to ≤ 10 mg/day oral prednisone or equivalent before atezolizumab can be resumed.^{a, b, c} 
The dose of cobimetinib can be reduced by 20 mg (one dose level) up to two times (i.e., from 60 mg to 40 mg and then from 40 mg to 20 mg). If further dose reduction is indicated after two dose reductions, the patient must discontinue cobimetinib but may continue treatment with atezolizumab at the investigator's discretion.
 
 • If cobimetinib is withheld for > 28 days because of toxicity, the patient should be discontinued from cobimetinib, unless resumption of treatment is approved by the Medical Monitor after discussion with the investigator. • After dose reduction, consideration may be given to allow for dose escalation of cobimetinib by a maximum of one dose level following resolution of the adverse event that resulted in dose modification, provided there are no safety concerns. • If atezolizumab is withheld for > 12 weeks because of toxicity, the patient should be discontinued from atezolizumab, unless resumption of treatment is approved by the Medical Monitor after discussion with the investigator.
IRRs, CRS, anaphylaxis, and hypersensitivity reaction	
 • Guidelines for management of IRRs and CRS are provided in the Atezolizumab Investigator's Brochure and Appendix 11 • For anaphylaxis precautions, see Appendix 7. • For severe hypersensitivity reactions, permanently discontinue all study treatment.

CRS = *cytokine-release syndrome*; IRR = infusion-related reaction.

^a If corticosteroids have been initiated, they must be tapered over ≥ 1 month to ≤ 10 mg/day oral prednisone or equivalent before atezolizumab can be resumed.

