Appendix 10 Management of Cobimetinib plus Atezolizumab-Associated Adverse Events (Arm A) (cont.)

HEPATOTOXICITY

Hepatotoxicity has been associated with the administration of atezolizumab and cobimetinib (see Section 5.1.1.2.1)

Patients with LFT abnormalities should be managed according to the guidelines in Table 2.

Table 2 Guidelines for Managing Atezolizumab and Cobimetinib–Associated Hepatotoxicity

Event	Action to Be Taken
Elevations in ALT, AST, and/or bilirubin	
AST/ALT > ULN to $\leq 3 \times$ ULN with total bilirubin < $2 \times$ ULN	
 • Continue atezolizumab and cobimetinib. • Continue with the standard monitoring plan (i.e., LFTs Q4W before dosing).
AST/ALT > $3 \times$ ULN to < $5 \times$ ULN with total bilirubin < $2 \times$ ULN	
 • Continue all study treatment. • Monitor LFTs at least weekly. • Consider referral to a hepatologist and liver biopsy. • For suspected immune-mediated events of > 5 days duration 
 – Consider withholding atezolizumab^c – Consider administering 1–2 mg/kg/day oral prednisone or equivalent followed by ≥ 1 month taper – Restart atezolizumab if event resolves to Grade 1 or better within 12 weeks^{a, b} – Permanently discontinue atezolizumab and cobimetinib if event does not resolve to Grade 1 or better within 12 weeks^{a, b, c}
AST/ALT > $5 \times$ ULN to < $10 \times$ ULN with total bilirubin < $2 \times$ ULN	
 • Continue all study treatment. • Monitor LFTs at least weekly. • Consider referral to a hepatologist and liver biopsy. • For suspected immune-mediated events: 
 – Withhold atezolizumab – Consider administering 1–2 mg/kg/day oral prednisone or equivalent followed by ≥ 1 month taper – If event does not improve within 48 hours after initiating corticosteroids, consider adding an immunosuppressive agent. If event resolves to Grade 1 or better, taper corticosteroids over ≥ 1 month. – Permanently discontinue atezolizumab and cobimetinib if event does not resolve to Grade 1 or better within 12 weeks^{a, b, c}

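### Appendix 10 Table 2 gives two different cobimetinib instructions for a recovered patient whose AST/ALT exceeded 10 × ULN and whose bilirubin exceeded 2 × ULN

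*Protocol*

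**What the plan says.** The Hepatotoxicity part of Protocol Appendix 10 makes its Table 2 the governing text for Arm A: "Patients with LFT abnormalities should be managed according to the guidelines in Table 2". Two of its rows matter here.

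- **Bilirubin row** (AST/ALT above 3 × ULN and bilirubin above 2 × ULN). Both drugs are withheld. On recovery: "Restart atezolizumab at fixed dose and cobimetinib at 1 dose reduction after discussion with medical monitor if AST/ALT < 3 × ULN". Bilirubin must also be back below 2 × ULN and the steroid dose below 10 mg prednisone equivalent a day. The exception is "Permanently discontinue atezolizumab and cobimetinib for life-threatening hepatic events, and contact the Medical Monitor".
- **Last row**, labelled "AST/ALT > 10 × ULN". Both drugs are stopped permanently. Footnote c is attached: "Resumption of atezolizumab may be considered in patients who are deriving benefit and have fully recovered from the immune-mediated event". It requires documented approval by the investigator and the Medical Monitor, and it does not name cobimetinib.

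The general guidance at the start of Appendix 10 adds two limits on cobimetinib. On dose: "If further dose reduction is indicated after two dose reductions, the patient must discontinue cobimetinib". On time: "If cobimetinib is withheld for > 28 days because of toxicity, the patient should be discontinued from cobimetinib", unless the Medical Monitor approves resumption. Section 4.6.2 lists the reasons for mandatory permanent discontinuation, among them "Any adverse event that requires study treatment discontinuation per the guidelines in Section 5.1, Appendix 10, and Appendix 11".

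**The concern.** The bilirubin row has no upper AST/ALT limit and the last row has no bilirubin limit, so a patient can belong to both. The three lower rows of the table all require bilirubin below 2 × ULN and therefore cannot overlap the bilirubin row. Only this pair lacks a boundary.

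If the two rows prescribed the same course, the overlap would be harmless. They part on cobimetinib after recovery. Two sites could then treat identical patients differently, each following a row that applies.

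The direction of the discrepancy is also awkward. Take two patients with the same AST/ALT above 10 × ULN. The one with normal bilirubin must stop cobimetinib. The one with bilirubin above 2 × ULN has a row that permits a restart. Section 5.3.5.7 regards raised transaminases combined with raised bilirubin as a sign of severe liver injury, although it measures transaminases against 3 × baseline and excludes cholestasis.

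**Working it through.** No sample size, power or error rate is involved. The check is one of row membership, followed by a comparison of instructions.

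**Step 1: which rows apply.** Let A be AST/ALT and B be bilirubin, both in multiples of ULN. The bilirubin row is A > 3 and B > 2. The last row is A > 10. Their intersection is A > 10 and B > 2, which is not empty. Test values, first as written and then with the bilirubin row capped at A ≤ 10:

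| A, B | Rows met as written | Number of rows as written | Number with cap |
|---|---|---|---|
| 12, 1 | last row | 1 | 1 |
| 12, 3 | bilirubin row and last row | 2 | 1 |
| 10.1, 2.1 | bilirubin row and last row | 2 | 1 |
| 10, 3 | bilirubin row | 1 | 1 |
| 8, 3 | bilirubin row | 1 | 1 |

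**Step 2: where the two rows agree for the 12, 3 patient.** Both take both drugs away immediately. Both end in a permanent stop if the event is life-threatening. Both leave a route back to atezolizumab, one through the restart clause and the other through footnote c.

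**Step 3: cobimetinib after recovery from an event that was not life-threatening.** Doses are 60, 40 and 20 mg, with at most two reductions. After a reduction, Appendix 10 and Section 5.1.5.1 allow re-escalation by one level, so a patient at 40 mg may already have used both reductions (60 to 40 to 20, then back to 40).

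| Dose at onset | Bilirubin row | Last row |
|---|---|---|
| 60 mg | 40 mg | stop |
| 40 mg, fewer than two prior reductions | 20 mg | stop |
| 40 mg, two prior reductions | stop | stop |
| 20 mg | stop | stop |

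The rows conflict only in the first two lines, where a reduction is still available.

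**Step 4: time off drug.** Those two lines assume either that cobimetinib was withheld for no more than 28 days or that the Medical Monitor approved resumption after a longer gap. Beyond 28 days without approval, both rows end in a stop. If steroids are given, the bilirubin row's taper of at least 1 month will normally pass 28 days, so approval would be needed. But the row asks only that steroids be considered, so recovery within 28 days without them remains possible.

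**Step 5: is there a tie-breaker?** Neither the table, its footnotes nor the general guidance ranks the rows. Section 5.1.5.1 Table 3, the general cobimetinib rule, restarts at 40 mg after a first Grade 3 or 4 event. It sends specific events to Appendix 10, so it does not decide the matter, but it shows that restart is a reading a site could reasonably adopt.

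**The case against.** The strongest reply is Section 4.6.2. Its list is mandatory, and meeting any one item is enough. AST/ALT above 10 × ULN is an event for which Appendix 10 demands permanent discontinuation, so on this view no ranking of rows is needed: meeting the last row settles it. The bilirubin row, moreover, does not oblige the Medical Monitor to agree to a restart, so stopping for good breaches neither row.

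Much of this stands. Section 4.6.2 does favour the permanent stop, and that is the reading the fix should adopt. It does not close the question, because it refers back to the same Appendix 10 guidance that points both ways for this patient. Footnote c also shows that a permanent stop under the table can be relaxed. A site that restarted cobimetinib after discussion with the Medical Monitor could cite an applicable row.

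A reader might infer that the table orders liver severity wrongly in general, treating patients with raised bilirubin too leniently. The documents do not support that. A patient at AST/ALT 8 and bilirubin 3 × ULN may restart while one at 12 and 1 must stop, and this remains so after the fix. That is a choice between two different patterns of injury, and the documents do not show it to be an error. The ordering argument holds only between patients who share AST/ALT above 10 × ULN and differ in bilirubin.

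A reader might also infer that every patient on 60 or 40 mg is caught. The 28-day rule and the limit of two reductions rule that out.

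**Conclusion.** The overlap is real and the text leaves it open. For a patient above both limits whose event was not life-threatening and has recovered, and who still has a cobimetinib reduction available, one row permits a restart one level lower and the other stops the drug permanently. The conclusion rests on reading each row by its stated limits and on taking footnote c at its word as covering atezolizumab only.

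The point is minor. A reader might infer an immediate safety hazard, but both rows take both drugs away at once, and AST or ALT above 10 × ULN is an event of special interest under Section 5.2.3, reportable within 24 hours. Only Arm A is concerned. I assume few patients; the documents give no rate for this liver pattern with the combination, so no frequency can be calculated. No endpoint or analysis changes. SAP Section 2.5 states that the study will be terminated early, so the practical benefit is confined to Arm A patients still on cobimetinib.

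**What to change.** Relabel the bilirubin row *AST/ALT > 3 to ≤ 10 × ULN with bilirubin > 2 × ULN*, and add one sentence saying that the row for AST/ALT above 10 × ULN applies whatever the bilirubin. Each patient above both limits then falls in one row, in line with Section 4.6.2. The sponsor's medical and safety leads should confirm the wording, since this is a clinical decision.

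The cost is one label and one sentence, with no new procedure. The downside is that a few recovered patients lose the option of restarting cobimetinib at a lower dose. A site clarification letter or the next amendment can carry the change; with early termination planned, an amendment for this alone is hard to justify.

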Appendix 10 Management of Cobimetinib plus Atezolizumab-Associated Adverse Events (Arm A) (cont.)

DERMATOLOGIC TOXICITY

Dermatologic toxicity and rash is associated with cobimetinib and atezolizumab (see Section 5.1.1.3.1) and should be managed according to the guidelines in Table 3.

Although uncommon, cases of severe cutaneous adverse reactions such as Stevens-Johnson syndrome and toxic epidermal necrolysis have been reported with atezolizumab.

Table 3 Guidelines for Managing Atezolizumab and Cobimetinib Rash

Event	Action to Be Taken
Dermatologic toxicity	
General guidance	
 A dermatologist should evaluate persistent and/or severe rash or pruritus. A biopsy should be considered unless contraindicated.
Dermatologic event, Grade 1 or 2	
 Continue atezolizumab and cobimetinib. Initiate supportive care (e.g., antihistamines, topical corticosteroids). If event does not improve, consider treatment with higher-potency topical corticosteroids. For Grade 2 rash, consider referral to dermatologist for evaluation and, if indicated, biopsy. 
Acneiform rash:
 
 Consider topical corticosteroids (e.g., hydrocortisone 2.5%, alclometasone) and oral antibiotics (minocycline, doxycycline, or antibiotics covering skin flora) as clinically indicated.

Appendix 10 Management of Cobimetinib plus Atezolizumab-Associated Adverse Events (Arm A) (cont.)

Table 3 Guidelines for Managing Atezolizumab and Cobimetinib Rash (cont.)

Event	Action to Be Taken
Dermatologic event, Grade 3	
 • Withhold atezolizumab and cobimetinib. • Refer patient to dermatologist for evaluation and, if indicated, biopsy. • Consider initiating treatment with 10 mg/day oral prednisone or equivalent, increasing dose to 1–2 mg/kg/day if event does not improve within 48–72 hours. • If event resolves to Grade 2 or better within 12 weeks, resume atezolizumab at fixed dose. If not, permanently discontinue atezolizumab and cobimetinib. ^{a, b} • Permanently discontinue atezolizumab and cobimetinib and contact Medical Monitor if event does not resolve to Grade 1 or better within 12 weeks. ^{a, b, c} • If event resolves to Grade 2 or better within 28 days, resume cobimetinib with dose reduced by one level. If not, permanently discontinue cobimetinib. 
Acneiform rash:
 
 • Consider continuation of topical corticosteroids (e.g., 2.5% alclometasone) and oral antibiotics (e.g., minocycline, doxycycline or antibiotics covering skin flora) when restarting cobimetinib.
Dermatologic event, Grade 4	
 • Permanently discontinue atezolizumab and cobimetinib, and contact Medical Monitor. ^c
Stevens-Johnson syndrome or toxic epidermal necrolysis (any grade)	
 • Follow guidelines for atezolizumab in Appendix 11. • Withhold cobimetinib. • If event resolves to Grade 1 or better, resume cobimetinib. 
Permanently discontinue cobimetinib if withheld for >4 weeks or if Stevens-Johnson syndrome or toxic epidermal necrolysis is confirmed.

^a If corticosteroids have been initiated, they must be tapered over ≥ 1 month to ≤ 10 mg/day oral prednisone or equivalent before atezolizumab can be resumed.

^b Atezolizumab may be withheld for a period of time beyond 105 days to allow for corticosteroids to be reduced to ≤ 10 mg/day oral prednisone or equivalent. The acceptable length of the extended period of time must be agreed upon by the investigator and the Medical Monitor.

^c Resumption of atezolizumab may be considered in patients who are deriving benefit and have fully recovered from the immune-mediated event. Patients can be rechallenged with atezolizumab only after approval has been documented by both the investigator (or an appropriate delegate) and the Medical Monitor.

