Appendix 10 Management of Cobimetinib plus Atezolizumab-Associated Adverse Events (Arm A) (cont.)

Table 1 Guidelines for Managing Atezolizumab- and Cobimetinib-Associated Gastrointestinal Toxicity (cont.)

Event	Action to Be Taken
Diarrhea, Grade 2 (intolerable) or Grade 3	
 • Withhold atezolizumab and cobimetinib. • Initiate supportive care and monitor patient closely. • Discontinue medications that may exacerbate colitis (e.g., NSAIDs) while investigating etiology. • Investigate etiology and refer patient to GI specialist for evaluation of possible colitis, including biopsy if appropriate. • If event resolves to Grade 1 or better within 12 weeks, resume atezolizumab at fixed dose. If not, permanently discontinue atezolizumab and cobimetinib. ^{a, b, c} • If event resolves to Grade 1 or better within 28 days, resume cobimetinib with the dose reduced by one level. If not, permanently discontinue cobimetinib.
Diarrhea, Grade 4	
 • Permanently discontinue atezolizumab and cobimetinib, and contact Medical Monitor. ^c • Initiate supportive care and monitor patient closely. • Discontinue medications that may exacerbate colitis (e.g., NSAIDs) while investigating etiology. • Rule out bowel perforation. • Investigate etiology, referring patient to GI specialist for evaluation of possible colitis, including biopsy if appropriate.
Colitis, Grade 1	
 • Continue atezolizumab and cobimetinib. • Initiate supportive care and monitor patient closely. • Discontinue medications that may exacerbate colitis (e.g., NSAIDs). • Refer patient to GI specialist for evaluation and confirmatory biopsy if symptoms persist for > 7 days.
Colitis, Grade 2	
 • Withhold atezolizumab and cobimetinib. • Initiate supportive care and monitor patient closely. • Discontinue medications that may exacerbate colitis (e.g., NSAIDs). • Refer patient to GI specialist for evaluation and confirmatory biopsy. • For recurrent events or events that persist >5 days, initiate treatment with 1–2 mg/kg/day oral prednisone or equivalent. • If event resolves to Grade 1 or better within 12 weeks, resume atezolizumab at fixed dose. If not, permanently discontinue atezolizumab and cobimetinib. ^{a, b, c} • If event resolves to Grade 1 or better within 28 days, resume cobimetinib with the dose reduced by one level. If not, permanently discontinue cobimetinib.

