Appendix 10 Management of Cobimetinib plus Atezolizumab-Associated Adverse Events (Arm A) (cont.)

PULMONARY EVENTS

Pneumonitis is associated with atezolizumab and cobimetinib (see Section Section 5.1.1.1.5 and should be managed according to the guidelines in Table 4.

Table 4 Guidelines for Managing Atezolizumab– and Cobimetinib–Associated Pulmonary Toxicity

Event	Action to Be Taken
Pulmonary events	
General guidance	
 Mild-to-moderate events of pneumonitis have been reported with atezolizumab and cobimetinib. All pulmonary events should be thoroughly evaluated for other commonly reported etiologies such as pneumonia/infection, lymphangitic carcinomatosis, pulmonary embolism, heart failure, chronic obstructive pulmonary disease, or pulmonary hypertension. For events concerning for pneumonitis, consider comprehensive infectious evaluation including viral etiologies.
Pneumonitis, Grade 1 (asymptomatic)	
 Continue atezolizumab and cobimetinib. Re-evaluate on serial imaging. Consider patient referral to pulmonary specialist.
Pneumonitis, Grade 2	
 Withhold atezolizumab and cobimetinib. Refer patient to pulmonary and infectious disease specialists and consider bronchoscopy or BAL. If bronchoscopy is consistent with immune-mediated etiology, initiate treatment with 1–2 mg/kg/day oral prednisone or equivalent. Resume atezolizumab and cobimetinib if event resolves to Grade 1 or better within 12 weeks.^{a, b} Permanently discontinue atezolizumab and cobimetinib and contact Medical Monitor if event does not resolve to Grade 1 or better within 12 weeks.^{a, b, c} For recurrent events, treat as a Grade 3 or 4 event.
Pneumonitis, Grade 3 or 4	
 Permanently discontinue atezolizumab and cobimetinib.^c Refer patient to pulmonary and infectious disease specialists and consider bronchoscopy or BAL. If bronchoscopy is consistent with immune-mediated etiology, initiate treatment with 1–2 mg/kg/day oral prednisone or equivalent. If pulmonary event does not improve within 48 hours or worsens, consider adding an immunosuppressive agent (e.g., infliximab, cyclophosphamide, IVIg, or mycophenolate). If event resolves to Grade 1 or better, taper corticosteroids over ≥ 1 month.

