Dermatologic event, Grade 2	
 • Continue atezolizumab. • Consider patient referral to dermatologist for evaluation and, if indicated, biopsy. • Initiate treatment with topical corticosteroids. • Consider treatment with higher-potency topical corticosteroids if event does not improve.
Dermatologic event, Grade 3	
 • Withhold atezolizumab for up to 12 weeks after event onset. ^a • Refer patient to dermatologist for evaluation and, if indicated, biopsy. • Initiate treatment with 10 mg/day oral prednisone or equivalent, increasing dose to 1–2 mg/kg/day if event does not improve within 48–72 hours. • If event resolves to Grade 1 or better, resume atezolizumab. ^b • If event does not resolve to Grade 1 or better while withholding atezolizumab, permanently discontinue atezolizumab and contact Medical Monitor. ^c
Dermatologic event, Grade 4	
 • Permanently discontinue atezolizumab and contact Medical Monitor. ^c

Appendix 11

Risks Associated with Atezolizumab and Guidelines for Management of Adverse Events Associated with Atezolizumab (cont.)

Table 9 Management Guidelines for Dermatologic Events (cont.)

Event	Management
Stevens-Johnson syndrome or toxic epidermal necrolysis (any grade)	
Additional guidance for Stevens-Johnson syndrome or toxic epidermal necrolysis:
 
 • Withhold atezolizumab for suspected Stevens-Johnson syndrome or toxic epidermal necrolysis. • Confirm diagnosis by referring patient to a specialist (dermatologist, ophthalmologist, or urologist as relevant) for evaluation and, if indicated, biopsy. • Follow the applicable treatment and management guidelines above. 
If Stevens-Johnson syndrome or toxic epidermal necrolysis is confirmed, permanently discontinue atezolizumab.

^a Atezolizumab may be withheld for a longer period of time (i.e., > 12 weeks after event onset) to allow for corticosteroids (if initiated) to be reduced to ≤ 10 mg/day oral prednisone or equivalent. The acceptable length of the extended period of time must be agreed upon by the investigator and the Medical Monitor.

^b If corticosteroids have been initiated, they must be tapered over ≥ 1 month to ≤ 10 mg/day oral prednisone or equivalent before atezolizumab can be resumed.

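### Appendix 10 Table 3 gives two different grades, Grade 2 and Grade 1, for the same 12-week decision on a Grade 3 dermatologic event

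*Protocol*

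**What the plan says.** The row for a Grade 3 dermatologic event in Protocol Appendix 10, Table 3 first withholds both drugs. Three of its bullets then govern restart and permanent stop:

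- Fourth bullet: "If event resolves to Grade 2 or better within 12 weeks, resume atezolizumab at fixed dose", followed by "If not, permanently discontinue atezolizumab and cobimetinib". Footnotes a and b are attached.
- Fifth bullet: "Permanently discontinue atezolizumab and cobimetinib and contact Medical Monitor if event does not resolve to Grade 1 or better within 12 weeks". Footnotes a, b and c are attached.
- Sixth bullet: "If event resolves to Grade 2 or better within 28 days, resume cobimetinib with dose reduced by one level", failing which cobimetinib is ended.

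For the same event, Appendix 11, Table 9 uses a single grade for atezolizumab: "If event resolves to Grade 1 or better, resume atezolizumab". If that grade is not reached while the drug is withheld, it is permanently stopped.

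Section 4.6.2 lists, among the reasons for mandatory permanent discontinuation, any adverse event that calls for it under Section 5.1, Appendix 10 or Appendix 11.

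**The concern.** The fourth and fifth bullets concern the same event, the same 12-week window and the same two drugs, but they set different grades. A patient who improves from Grade 3 to Grade 2 and no further by week 12 satisfies the condition to resume atezolizumab and also the condition to stop both drugs permanently. Because Section 4.6.2 makes the stop rules mandatory, two sites could treat the same case in opposite ways, and the bullets do not show which site has deviated.

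The stakes are patient safety and consistent conduct in Arm A. Which bullet is followed would also change the exposure data and the summary of adverse events leading to discontinuation.

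**Working it through.** No formula settles this; the check is a comparison of the texts.

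**Step 1: the two bullets against each possible best grade within 12 weeks.**

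| Best grade by week 12 | Fourth bullet | Fifth bullet | Agree? |
|---|---|---|---|
| Grade 1 or better | resume atezolizumab | no stop | yes |
| Grade 2 | resume atezolizumab; no stop of either drug | stop both permanently | no |
| still Grade 3 or higher | stop both permanently | stop both permanently | yes |

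One of the three outcomes receives opposite instructions.

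**Step 2: cobimetinib.** If Grade 2 is not reached by day 28, the sixth bullet ends cobimetinib by itself. The conflict therefore matters for cobimetinib in patients who reach Grade 2 by day 28, restart at a reduced dose, and have not reached Grade 1 by week 12. Appendix 10 does not say when the clocks start. Assuming that both run from event onset:

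- 12 weeks = 12 × 7 = 84 days.
- A restart on day d (d ≤ 28) leaves 84 − d days before the fifth bullet would apply.
- At the latest restart, d = 28, this is 84 − 28 = 56 days, or 56 / 28 = 2 cycles. On the 21/7 schedule that is 2 × 21 = 42 dosing days if there is no further interruption.
- An earlier restart gives a longer interval, so 56 days is the minimum and 84 days the ceiling.

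**Step 3: does the rest of Appendix 10 explain two grades?** Eight event rows set a 12-week permanent stop of atezolizumab by grade:

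- Table 1: diarrhoea Grade 2 intolerable or Grade 3; colitis Grade 2; colitis Grade 3 (3 rows)
- Table 2: AST/ALT above 3 to below 5 × ULN; above 5 to below 10 × ULN (2 rows)
- Table 3: dermatologic Grade 3 (1 row)
- Table 4: pneumonitis Grade 2 (1 row)
- Table 8: other treatment-related toxicity (1 row)

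The total is 3 + 2 + 1 + 1 + 1 = 8. Seven rows use one grade throughout; only the dermatologic row uses two. Its fifth bullet is word for word the stop sentence of the Grade 2 pneumonitis row, where the matching restart sentence carries the same grade: "Resume atezolizumab and cobimetinib if event resolves to Grade 1 or better within 12 weeks". Its fourth bullet follows the pattern of the diarrhoea and colitis rows, "If event resolves to Grade 1 or better within 12 weeks, resume atezolizumab at fixed dose. If not, permanently discontinue atezolizumab and cobimetinib", with the grade changed. This identifies the cell as an anomaly. It does not show which grade was intended.

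**Step 4: does any other provision settle it?**

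- Footnote a requires a corticosteroid taper before atezolizumab resumes. Footnote b allows a longer hold for that taper. Neither changes the grade.
- Footnote c allows rechallenge with atezolizumab after full recovery and documented approval. It is attached to the fifth bullet only.
- The Medical Monitor routes in the Appendix 10 general guidance and in Appendix 11 (Treatment Interruption) for a hold beyond 12 weeks cover atezolizumab only. The cobimetinib route covers a hold beyond 28 days.
- Appendix 11 Table 9 names one grade, but no order of precedence between the appendices is stated, and Section 5.1.5.3 sends dermatologic events to both.

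None of these says which grade applies at week 12.

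**The case against.** The strongest reply is that the bullets can be read in sequence: resume atezolizumab on reaching Grade 2, then stop both drugs if Grade 1 has not followed by week 12. The two stop clauses are nested, since a patient who fails Grade 2 also fails Grade 1, so both can be obeyed together. Under this reading the fourth bullet's stop clause is redundant, and redundancy is not contradiction. That much is fair: the direct clash is between the fourth bullet's restart and the fifth bullet's stop. But the text nowhere says that a restart at Grade 2 is provisional, and a patient who first reaches Grade 2 close to week 12 would be resumed and stopped at almost the same moment. The sequential reading is one a site might adopt, not one the protocol gives.

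Other points carry some weight:

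- The row above in Table 3 continues both drugs for Grade 1 or 2 events, which may explain why Grade 2 appears. That row is for events of that grade and does not address recovery from Grade 3.
- The restart is not unconditional, because footnotes a and b apply. The fifth bullet also requires contact with the Medical Monitor, which makes unnoticed divergence less likely. Neither supplies a default rule.
- Few patients may be involved. Section 5.1.1.3.1 reports about 16% of patients with Grade 3 or higher rash in a study of another cobimetinib combination, with about 90% of those events resolving. Applied to 225 Arm A patients, 225 × 0.16 × 0.10 = 3.6, or about 4. This borrows rates from another regimen. It counts unresolved events rather than events at Grade 2 at week 12, and gives no time to resolution, so the true figure could be higher or lower.
- SAP Section 2.5 says the study will be terminated early, which limits future exposure. It does not say that Arm A treatment has ended.

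**Conclusion.** The concern holds. As written, the cell gives opposite binding instructions to a patient whose best grade by week 12 is Grade 2, and nothing else in the protocol resolves them. The conflict is in current text and should be fixed.

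Its reach is limited to Grade 3 dermatologic events in Arm A that stay at Grade 2 at 12 weeks. The share of such events is not given, so the number of patients cannot be derived. The 56-day and 42-dose figures rest on the assumption that both clocks start at event onset. Nothing here bears on alpha, power or the PFS and OS analyses.

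**What to change.** The sponsor's clinical team must reconcile the fourth, fifth and sixth bullets of the Grade 3 dermatologic row in Appendix 10 Table 3 with each other and with Appendix 11 Table 9, so that one instruction applies at week 12. No grade is proposed here.

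A secondary improvement, on which the main point does not depend, is one sentence stating which appendix governs Arm A when both apply. It would also settle tolerable Grade 2 diarrhoea, where Appendix 10 Table 1 continues atezolizumab and Appendix 11 Table 3 withholds it.

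The cost is amended text for one table cell, one sentence on precedence, and a letter to sites with patients still on Arm A treatment. No new procedures are needed.
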